5.6.2.3.2 Malignancies

These events will be presented in the following tables:

- One table will be based on the criteria Standardized MedDRA Query (SMQ) = "Malignant or unspecified tumours (SMQ)"
- One table will be based on the criteria SMQ = "Malignant tumours (SMQ)".

SMQ search should include all TEAEs which code to a PT included in the Scope=Narrow group within each SMQ.

Confidential

Note that the events included in the "Malignancies" table will be a subset of the events included in the "Malignancies (including unspecified)" table. While the "Malignant tumours (SMQ)" is most relevant, "Malignant or unspecified tumours (SMQ)" must be reviewed for potential malignancies.

The output table will include 2 different overall incidence rows:

- tion The first overall incidence row will summarize "Any Malignancy" and this row will summarize the incidence of all AEs flagged for inclusion in the table (using the appropriate SMQ depending on the table), regardless of the High Level Term (HLT) it codes to.
- The second overall incidence row will summarize "Any Malignancy excluding non melanomic skin cancers HLT" and this row will summarize the incidence of AEs flagged for inclusion in the table (using the appropriate SMQ depending on the table). excluding those which code to an HLT of "Skin neoplasms malignant and unspecified (excl melanoma)".

5.6.2.3.3 Major adverse cardiac event

Potential cardiovascular events are adjudicated by the independent Cardiovascular Event Adjudication Committee (CV-CAC) according to the CV-CAC Charter (version 6.0). Adjudicated events are classified by the CV-CAC to one of the event types as defined in Table 6. The classification of an event as a Major Adverse Cardiac Event (MACE) is also determined by the CV-CAC. Events which are classified by the CV-CAC as any of the events types identified in the third column of Table 6 will be considered an extended MACE. Note that extended MACE is determined programmatically and includes a broader scope definition of MACE.

MACE as determined by the CV-CAC will be presented in a table and listing. Extended MACE will be presented separately in a table and listing.

Another table and listing will present the adjudicated cardiovascular events by type. For each cardiovascular event type, the individual PTs which fall within each event type will be summarized. This listing will indicate whether each event was determined to be a MACE and/or an extended MACE.

Additionally, a listing of all events identified for potential review by the CV-CAC will be produced. This listing will indicate whether each event was identified by the CV-CAC Chair for full committee review.

Event Type Code	Event Type	Extended MACE
1	Non-Fatal Myocardial Infarction (MI)	Yes
2	Non-Fatal Stroke: hemorrhagic	Yes
3	Non-Fatal Stroke: ischemic	Yes

Table 6: Cardiovascular event classifications

Event Type Code	Event Type	Extended MACE	
4	Non-Fatal Stroke: embolic	Yes	all o
5	Non-Fatal Stroke: undeterminable	Yes	
6	Hospitalization or ER for Unstable Angina with urgent revascularization	Yes	
7	Hospitalization or ER for Unstable Angina without urgent revascularization	No	
8	Hospitalization for Heart Failure	Yes O	
9	Transient Ischemic Attack (TIA)	No	
10	Coronary Revascularization Procedures (e.g. percutaneous coronary intervention, coronary artery bypass grafting)	Yes	
11	Urgent Revascularization Procedures (i.e. due to symptoms of brain ischemia or pending infarction)	Yes	
12	Arrhythmia (not associated with ischemia)	No	
13	Peripheral Arterial Event	No	
14	Venous Thromboembolic Event: pulmonary embolism (PE)	No	
15	Venous Thromboembolic Event: deep vein thrombosis (DVT)	No	
16	Venous Thromboembolic Event: PE and DVF	No	
17	Other CV Event	No	
18	Death due to Myocardial Infarction (MI)	Yes	
19	Death due to Stroke	Yes	
20	Sudden Cardiac Death	Yes	
21	Other CV Death (e.g. heart failure, pulmonary embolism, cardiovascular procedure-related)	Yes	
22	Cardiovascular: Undetermined Cause of Death (i.e. cause of death unknown)	Yes	
23	Non-Cardiovascular Death	No	
24	Non-Cardiovascular Event	No	
. 99	Inadequate information to adjudicate	No	

CV=Cardiovascular; DVT=Deep Vein Thrombosis; ER=Emergency Room; MACE= Major Adverse Cardiac Event; MI=Myocardial Infarction; PE=Pulmonary Embolism; TIA=Transient Ischemic Attack.

MACE is determined by the adjudication committee and is not identified programmatically based on event type.

5.6.2.3.4 Neutropenia

A table will be based on the following PTs (regardless of seriousness):

- Autoimmune neutropenia

- Band neutrophil count decreased
- Cyclic neutropenia
- Febrile neutropenia
- Idiopathic neutropenia
- Neutropenia
- Neutropenic infection
- Neutropenic sepsis
- Neutrophil count decreased _

5.6.2.3.5 Suicidal Ideation and Behavior

norization Potential neuropsychiatric events are adjudicated by the independent Neuropsychiatric Adjudication Committee according to the Neuropsychiatric Adjudication Committee (version 8.0). Adjudicated events are classified by the Committee as Suicidal or Non-suicidal. Adjudicated events are also further classified by the Committee to one of the event types as defined in Table 7. Suicidal Ideation and Behavior (SIB) is defined as events classified by the Committee as Suicidal.

A table and listing will present SIB events.

Another table and listing will present the adjudicated neuropsychiatric events by type. For each neuropsychiatric event type, the individual PTs which fall within each event type will be summarized. This listing will indicate whether each event was determined to be Suicidal or Non-Suicidal. For event type suicidal ideation, the listing will also indicate if intent was present and if the suicidal ideation was clinically significant.

Additionally, a listing of all events identified for potential review by the Committee will be produced. This listing will indicate whether each event was identified by the Neuropsychiatric Event Adjudication Committee Chair for full committee review.

Even t Type Code	Event Classification	Event Type
1	Suicidal	Suicidal events/completed suicide
2	Suicidal	Suicide attempt
3	Suicidal	Preparatory acts toward imminent suicidal behavior
40	Suicidal/Non- suicidal ^a	Suicidal ideation
7	Non-suicidal	Nonsuicidal Self-injurious behavior
8	Non-suicidal	Nonsuicidal Other
99	Not applicable	Inadequate information to adjudicate

Table 7: Neuropsychiatric event classifications

^a Suicidal ideation event types can be classified by the Neuropsychiatric Adjudication Committee as Suicidal or Non-suicidal depending on whether intent to die was present.

5.6.2.3.6 Inflammatory bowel disease

Selected gastrointestinal events are adjudicated by the independent Inflammatory Bowel Disease (IBD) Adjudication Committee (IBD-CAC) according to the IBD-CAC Charter (version 3.0). Adjudicated events are classified by the IBD-CAC into one of the diagnostic types as defined in Table 8. The events will further be classified as definite, probable or possible IBD.

An overview of adjudicated IBD events will be stratified by subjects with or without a previous medical history of IBD. Previous medical history of IBD will be determined using the information recorded on the Extra-Articular Assessment at Screening CRF page ("Does subject have a history of IBD?"). This overview table will present events adjudicated by the IBD-CAC as either possible, probable or definite IBD. Definite and probable IBD will also be aggregated and summarized in this table. In addition, this table will summarize each IBD event classification (possible, probable or definite) separately.

Another table and listing will present the adjudicated IBD events by type. For each IBD event type, the individual PTs which fall within each event type will be summarized.

Additionally, a listing of all events identified for potential review by the IBD-CAC will be produced. This listing will indicate whether each event was identified by the IBD-CAC Chair for full committee review.

A further supportive listing will present the individual diagnostic criteria met for each adjudicated IBD event.

Even	Event Type (Classification and diagnosis)	Classification
t Type Code	Rediten	
1	Possible Inflammatory Bowel Disease – Crohn's Disease	Possible
2	Probable Inflammatory Bowel Disease – Crohn's Disease	Probable
3	Definite Inflammatory Bowel Disease – Crohn's Disease	Definite
4	Possible Inflammatory Bowel Disease – Ulcerative Colitis	Possible
5	Probable Inflammatory Bowel Disease – Ulcerative Colitis	Probable
6	Definite Inflammatory Bowel Disease – Ulcerative Colitis	Definite
7	Possible Inflammatory Bowel Disease – type unclassified	Possible
80	Probable Inflammatory Bowel Disease – type unclassified	Probable
09	Definite Inflammatory Bowel Disease – type unclassified	Definite
10	Symptoms not consistent with Inflammatory Bowel Disease	Not applicable
11	Possible Inflammatory Bowel Disease – Microscopic Colitis	Possible
12	Probable Inflammatory Bowel Disease – Microscopic Colitis	Probable
13	Definite Inflammatory Bowel Disease – Microscopic Colitis	Definite

Table 8: IBD event classifications

Even	Event Type (Classification and diagnosis)	Classification	
Type Code			tion
14	Possible Inflammatory Bowel Disease – no further differentiation possible	Possible	of 12at
15	Probable Inflammatory Bowel Disease – no further differentiation possible	Probable	6
16	Definite Inflammatory Bowel Disease – no further differentiation possible	Definite	0
99	Not enough information to adjudicate	Not applicable	

Table 8: IBD event classifications

IBD=inflammatory bowel disease.

Note: IBD diagnoses of "microscopic colitis" and "no further differentiation possible" were added in an adjudication charter amendment, accounting for the event type numbering.

5.6.2.3.7 Hypersensitivity (including anaphylaxis)

A separate table will be prepared based on the MedDRA anaphylaxis Algorithm (see section 6.1.9) for acute anaphylactic events (reported on the same day as when an injection was administered or one day after). An AE glossary table will also be produced to summarize the MedDRA coding for these events. The glossary table will include the following fields: reported term, PT, LLT, HLT, and SOC.

A separate table will be prepared to summarize hypersensitivity events, identified using the SMQ "Hypersensitivity (SMQ)". All TEAEs which code to a PT included in the Scope=Narrow search will be included in this table. In addition, a separate table will be prepared to summarize serious hypersensitivity events, identified using the SMQ "Hypersensitivity (SMQ)". All serious TEAEs which code to a PT included in the Scope=Narrow search will be included in this table. An AE glossary table will also be produced to summarize the MedDRA coding for these events. The glossary table will include the following fields: reported term, LLT, PT, HLT, and SOC.

Furthermore, a separate table will be prepared to summarize injection site reactions, identified using the HLTs: "Administration site reactions NEC" and "Injection site reactions".

5.6.2.3.8 Hepatic events and DILI

A table for hepatic events will be created based on the SMQ of "Drug related hepatic disorders - comprehensive search (SMQ)". However, these 2 sub-SMQs are to be excluded: "Liver neoplasms, benign (incl cysts and polyps) (SMQ)" and "Liver neoplasms, malignant and unspecified (SMQ)". For each of the above SMQs, include all TEAEs which code to a PT included in the Scope=Broad and/or Scope=Narrow.

Note that all AEs meeting the above criteria are to be included. It should not be limited to events that the investigator determined to be related to study drug.

Cases of potential Hy's Law will be reported separately in a liver function test table.

In addition, potential Drug Induced Liver Injury (pDILI) events are adjudicated by the independent Hepatology Adjudication Committee (HAC) based on liver function test (LFT) elevations according to the HAC Charter (version 3.0). Adjudicated events will receive a causality assessment score as defined in Table 9 indicating the likelihood of the LFT elevations being a drug-induced liver injury related to the blinded investigational medicinal product.

A table will summarize the maximum final causality score and likelihood category for study participants with adjudicated events. Additionally, a listing of all study participants with events identified for potential review by the HAC will be produced. This listing will indicate the final causality assessment score. If a study participant has more than one causality assessment score, the worst score will be presented.

Causality Score	Numeric Causality Score	Likelihood (%)
Definite	1	>95
Highly likely	2	75-95
Probable	3	50-74
Possible	4	25-49
Unlikely	5	<25
Insufficient Data	99	NA

Table 0	Cancality	accoccment	coowing	her I	TAC fo	an duna	indu	and live	
I able 9		assessment	scoring	пу г	1AU II	or arug	-111010	сеа пуе	er minury
	~~~~~		~~~	~, -					

# 5.6.3 Additional Safety Assessments

# 5.6.3.1 Clinical laboratory evaluations

Laboratory values, including markedly abnormal laboratory values will be presented descriptively by treatment group for SS. Tables of markedly abnormal laboratory values (see section 6.1.7.1) and those based on CTCAE grade (see section 6.1.8) will only include selected variables.

# 5.6.3.1.1 Laboratory values over time

For tables where data are summarized by visit, unscheduled and repeat visits will not be summarized, but these data will be included in listings. For tables where multiple measurements over a period of time are considered (as in shift tables), unscheduled and repeat visits will be considered as long as they were collected in the period being summarized. All summaries will be presented in International System of Units and will be based on observed case values. In the case where laboratory values are below the LLQ, then these will be set to the midpoint between 0 and the lower limit of quantification for the purpose of summarizing the data.

The following summaries will be presented for data collected during the Treatment Period, SFU data will be included in listings only (unless otherwise specified).

- A summary of the absolute and change from Baseline values in each laboratory variable by treatment group and visit.
- A summary of the number and percentage of study participants experiencing markedly abnormal values at any time while on treatment (assessment on or following the first dose

of study treatment through to the end of the time at risk (see section 5.6.1)) by laboratory variable and treatment group

- A summary of the number and percentage of study participants with a given CTCAE grade (0,1,2,3, or 4) based on minimum/maximum post-baseline value by laboratory variable and treatment group
- A shift table of the number and percentage of study participants experiencing CTCAE grade 0,1,2,3, or 4 values (as applicable) at Baseline to maximum post-Baseline CTCAE grade, by laboratory variable and treatment group
- A figure presenting neutrophil CTCAE grade over time for study participants with at least one markedly abnormal neutrophil value (Grade 3 or above).
- Spaghetti plots presenting ALT values over time for study participants with at least one markedly abnormal ALT value (Grade 3 or above) (Including SFU).
- Spaghetti plots presenting AST values over time for study participants with at least one markedly abnormal AST value (Grade 3 or above) (Including SFU).
- A by-study participant listing of all laboratory data (including urinalysis) will be provided. This listing will be presented by treatment group and will include: center, subject identifier, age, sex, race, weight, visit, laboratory variable, result (with abnormal values flagged as "L" or "H" accordingly) and unit.

The table for elevated liver function tests (LFTs) will contain data beyond the CTCAE Grade 3 thresholds in order to allow for a more thorough review of elevated LFTs. There will be one table which will list the count and percentage of study participants meeting the below criteria at any time during the study:

- AST: >3xULN, >5xULN, >8xULN, >10xULN, >20xULN
- ALT: >3xULN, >5xULN, >8xULN, >10xULN, >20xULN
- AST or ALT: >3xULN, >5xULN, >8xULN, >10xULN, >20xULN
- Bilirubin: >1.5xULN, >2xULN
- ALP: >1.5xULN

The detailed information of markedly abnormal values criteria can be found in 6.1.7.1.

The following definition of potential drug induced liver injuries (pDILI) will be used:

- [AST  $\ge$  3xULN or ALT  $\ge$  3xULN] and Total Bilirubin  $\ge$  1.5xULN
- [AST  $\geq$ 3xULN or ALT  $\geq$ 3xULN] and Total Bilirubin  $\geq$ 2xULN
- [AST ≥3xULN or ALT ≥3xULN] and Total Bilirubin ≥2xULN in the absence of ALP ≥2xULN (Hy's law)

A table for potential drug induced liver injuries (pDILI) will be presented by treatment group for study participants with at least one post-Baseline liver laboratory assessment. Number and percentage of study participants meeting laboratory criteria for pDILI for at least 1 visit and reporting at least 1 symptom potentially associated with hepatitis or hypersensitivity according to

the Investigator on the pDILI CRF will be presented. Study participants who potentially meet Hy's law criteria at least 1 time during exposure. To be counted as potential Hy's Law, all criteria must be met at the same visit.

Two figures of evaluation of drug-induced serious hepatotoxicity (eDISH) will be created.

- eDISH for maximum Total Bilirubin (y-axis) versus maximum alanine/aspartate aminotransferase (ALT/AST), whichever is higher. Maximum bilirubin and maximum ALT/AST are values of each ULN on a log 10 scale.
- eDISH for maximum Total Bilirubin versus maximum alanine/aspartate aminotransferase (ALT/AST). In this figure, each participant is plotted based on their maximum concurrent total bilirubin (y-axis) and transaminase (ALT or AST, whichever is higher), where maximum concurrent is defined as maximum total bilirubin elevation occurring on or within 30 days after the maximum ALT or AST elevation. The transaminase elevation has to occur first.

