1.3 Schedule of activities

Table 1-1: Schedule of study assessments

Protocol activity	Visit ^a / Week	Treatment Period							SFU ^c
		Screening ^b	Baseline (W0)	W1	W2	W4	W8	W12	
Informed consent	X								
Inclusion/exclusion	X	X							
Urine drug screen	X								
Demographic data	X								
PSO history	X								
Significant past medical history and concomitant diseases	X	X ^d							
Physical examination ^{e, f}	X	X					X	X	X
Height		X							
Body weight		X						X	
Vital signs ^g	X	X	X	X	X	X	X	X	X
Hematology and biochemistry	X	X	X	X	X		X	X	X
Urinalysis	X	X						X	X
ECG	X							X	
Pregnancy testing ^h	X	X			X	X	X	X	X
Hepatitis B and C testing ⁱ	X								
HIV testing ^j	X								
Chest x-ray ^k	X								

Table 1-1: Schedule of study assessments

Protocol activity	Visit ^a / Week	Treatment Period							SFU ^c	
		Screening ^b	Baseline (W0)	W1	W2	W4	W8	W12		W16/ PEOT
IGRA TB test		X								
TB questionnaire ^l		X	X					X ^l		X
PASI		X	X	X	X	X	X	X	X	X
IGA		X	X	X	X	X	X	X	X	X
Scalp IGA ^m			X		X	X	X	X	X	X
Percentage of BSA		X	X	X	X	X	X	X	X	X
DLQI			X		X	X	X	X	X	
PHQ-9		X	X			X	X	X	X	X
C-SSRS		X	X			X	X	X	X	X
PSD (P-SIM) (daily)		X	X	X	X	X	X	X	X	
Concomitant medication		X	X	X	X	X	X	X	X	X
AEs		X	X	X	X	X	X	X	X	X
IRT ^{n, o}		X	X	X	X	X	X	X	X	X
Blood sample for PK plasma BKZ concentrations and anti-BKZ antibodies ^p			X			X	X	X	X	X
BKZ or placebo administration ^{n, o}			X			X	X	X		

AEs=adverse events; BKZ=bimekizumab; BSA=body surface area; DLQI=Dermatology Life Quality Index; ECG=electrocardiogram; eCRF=electronic Case Report Form; C-SSRS=Columbia Suicide Severity Rating Scale; HBcAb+=positive for anti-hepatitis B core antibody; HBsAg+=positive for hepatitis B surface antigen; HCV=hepatitis C virus; HIV=human immunodeficiency virus; IGA=Investigator’s Global Assessment; IGRA=interferon-gamma release assay; IMP=investigational medicinal product; IRT=interactive response technology; MAP=Managed Access Program; PASI=Psoriasis Area Severity Index; PEOT=Premature End of Treatment; PHQ-9=Patient Health Questionnaire-9; PK=pharmacokinetic; PSD=patient symptom diary; P-SIM=Patient Symptom and Impact Measure; PSO=psoriasis; SFU=Safety Follow-Up; TB=tuberculosis; W=Week

- ^a Visit windows of ± 3 days from the first dose (W0) to the Week 16 visit. The SFU Visit window is ± 7 days from last dose.

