#### Potentially Clinically Significant Criteria for Safety Endpoints 6.1.7

#### 6.1.7.1 Markedly abnormality criteria for laboratory data

Markedly abnormal values are defined as those with a severity of Grade 3 and above based on the common terminology criteria for adverse events (CTCAE) criteria (U.S. Department of Health and Human Services 2017). Definitions of markedly abnormal values using the Grade 3 cut points are given in the tables below for age ranges of  $\geq 17$  years (Table 10 for markedly abnormal hematology values, Table 11 for markedly abnormal biochemistry values, and Table 12 for markedly abnormal liver function test values). Tables summarizing markedly abnormal values should include a summary (counts and percentages) of markedly abnormal labs observed at any time while on treatment (i.e., treatment-emergent markedly abnormal [TEMA]). For this summary, Baseline values are not considered. The laboratory results classified as Grade 3 or Grade 4 will be summarized and listed separately.

Parameter	Co	nventional	s s	Abnormal	
name	Unit	Criteria	Unit	Criteria	Designation
Hemoglobin	/ 17	<8.0+	/ T	<8.0	AL
	g/dL	>4.0 above ULN	g/L	>4.0 above ULN	AH
Lymphocytes		<0.5	109/J	<0.5	AL
Absolute	10 ⁻⁷ L	>20.0	10 ² /L	>20.0	AH
Neutrophils Absolute	10 ⁹ /L	<1.0	10 ⁹ /L	<1.0	AL
Platelets	10 ⁹ /L	<50	10 ⁹ /L	<50	AL
WBC/Leukocytes	10 ⁹ /L	<2.0	10 ⁹ /L	<2.0	AL
y		>100		>100	AH

normal Hematology Values
n

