# Table 15: Definitions of CTCAE grades by hematology parameter

Parameter (unit)	Definition	Unit	Grade 1	Grade 2	Grade 3	Grade 4
Hemoglobin	Low	g/L	100- <lln< td="">80-<100	<80	N/A	</lln<>	80-<100	<80	N/A
Hemoglobin	High	g/L	>0-20 above BL	>20-40 above BL	>40 above BL	N/A
Platelets	Low	10 ⁹ /L	75- <lln< td="">50-<75	25-<50	<25	</lln<>	50-<75	25-<50	<25
WBC	Low	10 ⁹ /L	3- <lln< td="">2-<3	1-52	<1	</lln<>	2-<3	1-52	<1
WBC	High	10 ⁹ /L	N/A	N/A	⊘100	N/A
Lymphocytes	Low	10 ⁹ /L	0.8- <lln< td="">0.5-<0.8	0.2-<0.5	<0.2	</lln<>	0.5-<0.8	0.2-<0.5	<0.2
Lymphocytes	High	10 ⁹ /L	N/A	>4-20	>20	N/A
Neutrophils	Low	10 ⁹ /L	1.5- <lln< td="">S1.0-<1.5	0.5-<1.0	<0.5	</lln<>	S 1.0-<1.5	0.5-<1.0	<0.5

Note that study participants who meet the decreased potassium criterion of 3.0< LLN, which is specified as the decreased potassium lab criterion for both CTCAE Grade 1 and Grade 2, will be counted as Grade 2.

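### SAP Table 15 grades high hemoglobin by the rise above Baseline while Table 10 measures it from the ULN, so normal-range rises count as Grade 1 and Grade 3 does not match markedly abnormal

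*SAP*

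**What the plan says.** SAP 6.1.7.1 ties two sets of tables together: "Markedly abnormal values are defined as those with a severity of Grade 3 and above based on the" CTCAE criteria. Table 10 then gives the markedly abnormal high cut point for hemoglobin as ">4.0 above ULN". It prints that same figure under both g/dL and g/L, and likewise prints 8.0 as the low limit under both units.

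SAP 6.1.8, Table 15, grades high hemoglobin in g/L. A rise above 0 and up to 20 over BL is Grade 1, ">20-40 above BL" is Grade 2, and a rise of more than 40 over BL is Grade 3. There is no Grade 4. BL is missing from the SAP's list of abbreviations, and Baseline is the only natural reading.

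SAP 5.6.3.1.1 uses these grades twice for the Treatment Period. One table counts participants by grade "based on minimum/maximum post-baseline value by laboratory variable and treatment group". The other is the shift table of participants "experiencing CTCAE grade 0,1,2,3, or 4 values (as applicable) at Baseline to maximum post-Baseline CTCAE grade". The same section requires summaries in SI units. SAP 5.6.3.1 limits the markedly abnormal and grade tables to selected variables; hemoglobin is listed in both Table 10 and Table 15.

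**The concern.** A toxicity grade for a high value should say how far the value lies above normal. Table 15 instead says how far it lies above the participant's own starting point, wherever that was. Three things follow from the text without any assumption about the data.

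- A participant who moves up by 1 g/L well inside the normal range is Grade 1.
- The Baseline side of the high-hemoglobin shift carries no information, because the rise over Baseline is zero at Baseline. A participant who enters above the ULN is still Grade 0.
- Grade 3 and markedly abnormal, which 6.1.7.1 treats as the same thing, have different reference points and can disagree in both directions.

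At stake is whether the high-hemoglobin rows of two planned safety tables can be read. They would mostly show ordinary within-person variation labelled as a graded abnormality.

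**Working it through.** The plan states no figure for the share of participants graded, so there is none to reproduce.

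**1. Tables 14 and 15 compared.** The High rows for creatinine, sodium, potassium, calcium, magnesium and cholesterol start at the ULN. Triglycerides (1.71 mmol/L), WBC (100 × 10⁹/L) and lymphocytes (4 × 10⁹/L) start at fixed limits. Hemoglobin alone starts at BL.

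**2. Baseline grade.** Rise at Baseline = Baseline − Baseline = 0, which is not above 0. Every participant is Grade 0 in this direction.

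**3. Grade 3 against markedly abnormal.** Assume a ULN of 160 g/L (the documents give none). Read Table 10 both as printed in g/L (4.0) and as converted from g/dL (4.0 g/dL = 40 g/L).

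| Baseline | Later | Rise over Baseline | Table 15 | Relative to ULN | Table 10, 4.0 g/L | Table 10, 40 g/L |
|---|---|---|---|---|---|---|
| 115 | 158 | 43 | Grade 3 | −2 | no | no |
| 175 | 205 | 30 | Grade 2 | +45 | yes | yes |

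Both disagreements hold whichever unit column is used. The only hemoglobin limit in Protocol 5.2 is a floor of 8.5 g/dL, so neither Baseline is excluded by it.

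**4. Share at Grade 1 or worse with no drug effect.** The "Hematology and biochemistry" row in Protocol Table 1-1 gives five post-Baseline samples in the Treatment Period: Weeks 1, 2, 4, 12 and 16, with Week 8 blank. Baseline is a single value (SAP 5.1.1.1.5). If Baseline and k post-Baseline values are exchangeable and untied,

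P(maximum post-Baseline > Baseline) = k/(k + 1).

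- k = 5: 5/6 = 83.3%, that is 25 of 30 on bimekizumab and 12.5 of 15 on placebo.
- k = 4: 4/5 = 80.0%. k = 6: 6/7 = 85.7%. A larger k is possible because for tables such as shift tables "unscheduled and repeat visits will be considered as long as they were collected in the period being summarized".

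**5. Sensitivity.** The within-person SD and any drift are assumptions. Values were recorded to 1 g/L, with 300,000 participants simulated per scenario.

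| Scenario | Grade 1 or worse |
|---|---|
| SD 3 / 4 / 5 / 6 / 8 g/L | 79.4 / 80.5 / 81.1 / 81.5 / 81.9% |
| SD 5, 10% of visits missed | 79.3% |
| SD 5, weekly autocorrelation 0.5 / 0.8 / 0.9 | 82.0 / 81.2 / 79.3% |
| SD 5, drift −5 / −3 / −2 g/L | 51.7 / 64.7 / 70.7% |
| SD 5, drift +2 g/L | 89.0% |

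Without drift the range is 79-83%. At 79.4% the counts are 0.794 × 30 = 23.8 and 0.794 × 15 = 11.9.

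**6. Which grades are inflated.** Without drift, Grade 2 or worse is about 0.8% at SD 5 and 12% at SD 8. Grade 3 is at most about 0.1%.

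**7. Units.** For an assumed Baseline of 145 and ULN of 170 g/L, the Grade 3 or markedly abnormal cut point is 145 + 40 = 185 under Table 15, 170 + 40 = 210 under Table 10 in g/dL, and 170 + 4 = 174 under Table 10 in g/L as printed. That is three thresholds for one definition.

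**The case against.** The strongest case against is that this is a table-consistency matter of small practical weight. The laboratory summaries are descriptive and the laboratory endpoints tertiary. The inflation affects both arms alike and is almost all Grade 1, so conflicts at Grade 3 would be rare among about 45 participants. All of that stands.

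It can also be said that the documents do not settle which reference is right. The SAP cites CTCAE version 5.0 but does not reproduce it. Its version history lists an update to Section 6.1.8 in Amendment 1, so Table 15 may be the newer text. This stands too: the case rests on the SAP disagreeing with itself, not on an outside standard. It does not rescue Table 15 as written, because its rule leaves the Baseline grade empty and separates Grade 3 from markedly abnormal.

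A reader might infer that true rises above normal would be hidden. They would not be: 5.6.3.1.1 also plans absolute and change-from-Baseline summaries, a separate markedly abnormal table and listings with high values flagged. A reader might also infer that the whole hemoglobin shift is empty at Baseline. Only the high direction is; low hemoglobin is graded on absolute values.

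**Conclusion.** The inconsistency is real and follows from the text alone: Table 15 uses Baseline, Table 10 uses the ULN, and 6.1.7.1 makes the two the same threshold. The Grade 1 inflation is also real, but its size depends on assumptions. It is about 79-83% of participants in either arm if values are exchangeable with no drug effect, and about 52% to 89% for drifts from −5 to +2 g/L.

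The documents give no hemoglobin SD or drift, so a flat statement that four in five participants would be graded is more than they support. They also do not support reading this as a bias between arms, since the no-effect inflation is the same in both. The high-hemoglobin rows become hard to interpret; no efficacy result and no other laboratory parameter is affected. It should be corrected before the tables are produced.

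**What to change.** Use one reference and one unit for high hemoglobin in both tables. The ULN is the better choice because it matches Table 10 and the pattern of the other High rows, and it gives Baseline a meaningful grade.

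- **Table 15:** set Grade 1 at more than 0 and up to 20 g/L above the ULN, Grade 2 at more than 20 and up to 40, and Grade 3 at more than 40. Apply this to Baseline and post-Baseline values in both the grade summary and the shift table.
- **Table 10:** correct the g/L column to 80 (low) and 40 above the ULN (high), in line with Table 15. Changing Table 15 alone would leave a tenfold mismatch, because summaries are in SI units.
- **If a Baseline reference is kept for any case:** define BL and limit it to participants whose Baseline is above the ULN.

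The cost is three cells in Table 15, two in Table 10 and the matching programming. No new data are needed, and only descriptive safety tables change.
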